1. **30-day follow-up:** should be performed for all recruited patients. Each patient will be followed-up for 30 days starting on the day of surgery (day 0).
2. **One-year follow-up:** due to the nature of the study, aiming to assess bile duct injury and unsuspected gallbladder cancers, we aim to collect one-year follow-up data on all recruited patients. Each patient will be followed-up for one year starting on the day of surgery (day 0). Patients are excluded from one-year follow-up if they had died within 30 days of index surgery, as there would be no additional data to collect from these patients since the 30-day follow-up that had already been completed previously. Additional collaborators can be recruited to aid one-year follow-up data collection once the follow-up period begins (31st Jul 2024).

Local arrangements for successful 30-day and one-year follow-up may include: reviewing patient notes, reviewing patient status in outpatient clinics or via telephone interview at 30 days (if this is normal practice) and checking for readmission through handover lists. Follow-up should be performed in line with current routine practices of each hospital. No additional telephone, in-person or questionnaire-based follow-up is required. Source data may be acquired from hospital in-patient notes, clinical electronic systems, or outpatient letters.

Key to successful 1-year follow-up:

1. *Ensure you keep a list of all patient ID and corresponding RedCap ID in a safe, secure computer to allow follow-up of these patients. This will be in the form of an encrypted spreadsheet held securely on the local hospital computer network by a member of the data collection team (a hospital lead, supervising consultant/attending, or audit officer).*
2. *Where it is anticipated that a hospital lead will rotate to another hospital, then the supervising consultant should facilitate the secure storage of patient ID and corresponding RedCap ID.*
3. *Ensure the audit office / local governing bodies are clear this will be a follow-up study.*
4. *In high-volume centres where achieving high data completeness may be burdensome, involvement additional team members to provide support can be permitted.*

Table 1: Data collection periods

Dates	Description
00:00 31 st July – 23:59 13 th Aug 2023	Start of data collection period 1 (+ 30-day follow-up: ends 12 th Sep 2023) (+ one-year follow-up: ends 13 th Aug 2024)

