The secondary endpoints include:

- Rates of achieving a critical view of safety.
- Rates of different bailout procedures initiated when safe cholecystectomy is compromised.
- 30-day and one-year rates of textbook outcomes [2] for cholecystectomy, which covers: postoperative complications (Clavien-Dindo classification), intraoperative complications (including bile duct and vascular injuries), length of stay, readmission, mortality, and postoperative imaging or intervention.
- Unsuspected gallbladder cancer rates and their 30-day and one-year outcome rates, which includes: (1) complication rates (Clavien-Dindo classification); (2) time-to-recurrence rates (time from surgery to recurrence); and (2) revisional surgery rates (liver resection, bile duct resection and/or lymph node dissection).
- A description of the global variation in the availability of cholecystectomy services, training and sustainable practice.

Control of Bias and Confounding

Data will be collected on audit standards and confounding factors for risk-adjusted analyses. These include age, sex, body mass index, American Society of Anaesthesiologists (ASA) grade, and relevant comorbidities. Variables including operative urgency, operative contamination, and operative approach will also be collected. Without appropriately adjusting for risk factors, it is likely that any findings would be biased and unable to be appropriately analysed on an international scale. A full list of required data fields is available in **Appendix B**, and on the REDCap database.

Data Analysis & Sample Size

Variation across different international health settings will be tested using the human development index (HDI) countries [17] a composite statistic of life expectancy, education and income indices published by the United Nations. Initially, data will be reported using descriptive analyses. Comparisons between groups will be undertaken using appropriate parametric and non-parametric analyses. Multilevel logistic regression multivariate models will be constructed to account for case mix, with population stratification by hospital and country as random effects.

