8. Operation performed	Standard total cholecystectomy Total cholecystectomy by the fundus-first (top down) approach Subtotal cholecystectomy (reconstituting / fenestrated) Not performed (diagnostic laparoscopy / cholecystostomy) Definitions of subtotal cholecystectomy: 
 Fenestrated: does not occlude the gallbladder but may suture the cystic duct internally Reconstituting: closes off the lower end of the gallbladder, creating a remnant gallbladder
9. Abdominal drain insertion	Yes / No
10. Anatomical Biliary variant	Yes / No
11. Intraoperative CBD Assessment	Intraoperative cholangiogram (IOC) / Incisionless fluorescent cholangiography/ Laparoscopic ultrasound / Intraoperative ERCP If yes to any of the above: 
 Decision: Selective / Routine. If selective, state Indication: Raised liver function test / Concern of a bile duct injury / pre-operative imaging suggestive of CBD stone Findings: Stone / No stone. If stone, tick all that apply for management: Flushing with saline and smooth muscle relaxant / Fogarty catheter trawl / Basket retrieval / Choledochoscope / No intraoperative treatment attempted
12. Common Bile Duct exploration	Yes (Trancystic / Choledochotomy) / No If Choledochotomy then select closure: Primary closure / T-tube
13. Operative contamination	Clean (Gastrointestinal (GI) and genitourinary (GU) tract not entered) Clean-Contaminated (GI or GU tracts entered but no gross contamination) Contaminated (GI or GU tracts entered with gross spillage or major break in sterile technique) Dirty (There is already contamination prior to operation, e.g., faeces or bile).
14. Intraoperative complications - excluding bile duct injury (BDI) (Select all that apply)	Bile spilt / Stones Spilt / Bleeding / Major vascular injury / Bowel injury
15. Were reusable gowns used in this procedure?	Yes (All scrubbed staff/ some scrubbed staff) / No
16. Were reusable drapes used in this procedure?	Yes / No
30-day Outcomes	Required data (definition / comment)
1. Highest 30-day Clavien-Dindo (CD) Grade	0 / I / II / IIIa / IIIb / IVa / IVb / V (Appendix D for definitions) If CD IIIa: Radiological drainage (yes / No) If CD IIIb: Re-laparoscopy (yes / No) If CD V (death): please indicate time from index cholecystectomy to death: number of days (whole number, 0 = same day)

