2. Unplanned critical care admission - where critical care admission was not part of pre-operative plan	Yes / No If yes, please indicate length of stay in critical care: number of days (whole number)
3. Unplanned Re-imaging - where imaging in post-operative period (e.g.,	Yes / No If yes then tick all that apply: USS / CT / MRI / ERCP

CT, MRCP) was not part of pre-operative plan
	

4. 30-day postoperative complications (Select all that apply)
	
Surgical site infection (CD Grade* 0 / I / II / IIIa / IIIb / IVa / IVb / V) Postoperative pulmonary complications (CD Grade* 0 / I / II / IIIa / IIIb / IVa / IVb / V) Bile leak (CD Grade* 0 / I / II / IIIa / IIIb / IVa / IVb / V) Bleeding (CD Grade* 0 / I / II / IIIa / IIIb / IVa / IVb / V) Intra-abdominal collection (CD Grade* 0 / I / II / IIIa / IIIb / IVa / IVb / V) Acute pancreatitis (CD Grade* 0 / I / II / IIIa / IIIb / IVa / IVb / V) *For all of the above, please indicate the Clavien-Dindo grade associated with that complication

5. Length of stay
	
Whole number of days (Where discharge < 23 hours, enter 0. If the patient has not been discharged prior to the end of 30-day follow-up, enter '31')

6. Unplanned readmission within 30 days
	
Yes (Length of stay) / No

Bile Duct Injury (BDI) data fields
	
Required data (definition / comment)

1. BDI identified within 30-days of index cholecystectomy
	
Yes / No If yes: please fill in the rest of the data points below. If No: Was BDI identified within one-year of index cholecystectomy: Yes / No (if yes, then please fill in the rest of the data points below)

2. Presentation of BDI
	
Intraoperatively / Controlled bile leak from surgically placed abdominal drain / Abdominal pain due to uncontrolled bile leak / Obstructive jaundice or cholangitis / Intra-abdominal abscess or biloma

3. Days from index cholecystectomy to diagnosis
	
Number of days (0 = intraoperatively)

4. Bile duct injury grade
	
A / B / C / D / E1 / E2 / E3 / E4 / E5 (Strasberg Injury Grade: Appendix D for definition)

5. Concomitant vascular injury
	
Yes (Right hepatic artery / Common hepatic artery / Main portal vein / Right portal vein) / No

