3. TNM grade (AJCC 8th edition) (Appendix D for definition)	
T category: Tis / T1a (lamina propria) / T1b (muscularis) / T2a (peritoneal side) / T2b (hepatic side) / T3 / T4
 
N category: N0 / N1 (1-3 nodes) / N2 (>3 nodes)
 
M category: M0 / M1

4. Discussed at MDT	Yes / No
5. Adjuvant treatment	No / Chemotherapy / Radiotherapy
6. Revisional surgery completed	
Yes / No (not required) / No (unresectable tumour)
 
 • If yes, type of surgery (select all that apply): Liver resection (liver bed / one segment / two segments/ ≥ 3 segments) / bile duct resection / lymph node dissection • If yes, time from histology result to revisional surgery: Number of days (whole number)
7. Pathology results if revisional surgery	
Resection margin status: R0 / R1 / R2
 
Lymphovascular invasion: Yes / No
 
Perineural invasion: Yes / No
 
Resection margin definition: R0 = microscopically negative for residual tumor; R1 = microscopically margins still demonstrate the presence of tumor; R2 = macroscopically-visible disease remains post-surgery.

8. Recurrence on imaging at one year	
Yes / No
 
If yes, time from surgery to recurrence: number of days (whole number)

One-year Outcomes	Required data (definition / comment)
1. Highest one-year Clavien-Dindo (CD) Grade	
0 / I / II / IIIa / IIIb / IVa / IVb / V
 
If CD IIIa: Radiological drainage (yes / No)
 
If CD IV: Re-laparoscopy (yes / No)
 
If CD V (death): please indicate time from index cholecystectomy to death: number of days (whole number)

2. Readmissions	Total number of readmissions

3. One-year complications
(Select all that apply)

Surgical site infection (CD Grade* 0 / I / II / IIIa / IIIb / IVa / IVb / V)

Postoperative pulmonary complications (CD Grade* 0 / I / II / IIIa / IIIb / IVa / IVb / V)

Bile leak (CD Grade* 0 / I / II / IIIa / IIIb / IVa / IVb / V)

Biliary stricture (CD Grade* 0 / I / II / IIIa / IIIb / IVa / IVb / V)

Bleeding (CD Grade* 0 / I / II / IIIa / IIIb / IVa / IVb / V)

Intra-abdominal collection (CD Grade* 0 / I / II / IIIa / IIIb / IVa / IVb / V)

Acute pancreatitis (CD Grade* 0 / I / II / IIIa / IIIb / IVa / IVb / V)

*For all of the above, please indicate the Clavien-Dindo grade associated with that complication

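### The one-year textbook outcome cannot be computed on its listed components: imaging is not collected after day 30 for the general cohort, and readmission changes definition

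*Protocol*

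**What the plan says.** Statistical Considerations, Secondary Outcome Measures, names as an endpoint the "30-day and one-year rates of textbook outcomes [2] for cholecystectomy". A single list of components follows and serves both time points: postoperative complications by Clavien-Dindo (CD) grade, intraoperative complications, and then "length of stay, readmission, mortality, and postoperative imaging or intervention".

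Appendix B (Data Dictionary) has six 30-day outcome fields. One is "Unplanned Re-imaging - where imaging in post-operative period" outside the preoperative plan, with modality. Another is a yes/no item restricted to unplanned readmission in the first 30 days.

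The one-year section has three fields: "1. Highest one-year Clavien-Dindo (CD) Grade", then "Total number of readmissions", then a list of complications each with its CD grade. Section 6 of the CRF (Appendix A) has the same three.

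On re-operation, the 30-day dictionary has "If CD IIIb: Re-laparoscopy (yes / No". The one-year dictionary places "Re-laparoscopy (yes / No" under CD IV. The CRF asks about re-operation at IIIb at both time points.

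On early deaths, Follow-up Period states: "Patients are excluded from one-year follow-up if they had died within 30 days of index surgery". The reason given is that nothing further remains to be collected from them.

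**The concern.** A composite reported at two time points under one definition invites a comparison of the two rates. That comparison is sound only if each component is observed in the same way at both. Here one component is not observed after day 30 in most of the cohort, and another is observed under a wider definition. A difference between the two rates would then mix true late failures with a change in what the forms ask.

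The gap lies in data capture. Control of Bias and Confounding refers the reader to Appendix B for the complete set of data fields, and Data Governance says the dictionary was created before data collection began. A separate analysis plan can define an algorithm, but it cannot recover information that no form requests.

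The protocol also intends comparisons across Human Development Index groups. If use of planned readmission or late imaging differs between health systems, the one-year contrast between groups would be affected too.

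**Working it through.** The plan gives no figure for this endpoint, so there is none to reproduce. The check sets each component against the fields that would supply it (CRF Sections 2 to 6; Appendix B).

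| Component | 30-day source | One-year source | Same definition? |
|---|---|---|---|
| Postoperative complications | Highest CD grade; graded list | Highest CD grade; graded list (biliary stricture added) | Essentially yes |
| Intraoperative complications | Operative fields; bile duct injury section | Operative fields reused; bile duct injury section extends to one year | Yes |
| Length of stay | Index stay | Reused | Yes |
| Mortality | CD V with day of death | CD V with day of death; 30-day deaths already held | Yes |
| Readmission | Unplanned, yes/no | Count of all readmissions, no window | No |
| Imaging | Unplanned re-imaging, yes/no | None for the general cohort | Cannot be evaluated |
| Intervention | CD grade | CD grade | Yes |

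**Imaging.** The only other postoperative imaging items belong to the bile duct injury and histology sections, so they cover patients with an injury or a malignancy. CD grade cannot stand in for imaging: Appendix D counts therapeutic endoscopy and interventional radiology as IIIa but tells collectors to leave out diagnostic procedures. What goes unrecorded is therefore unplanned imaging or diagnostic ERCP after day 30, without an intervention, in a patient with neither bile duct injury nor cancer.

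**Readmission.** The one-year count can be cut at 0 versus 1 or more, but planned admissions cannot then be removed. The protocol itself foresees some: revisional surgery after malignant histology has its own field. The document also does not say whether the count starts at surgery or at day 31.

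**Re-operation prompt.** CRF at one year: IIIb. Dictionary at one year: CD IV. Under the dictionary, a IIIb patient is not asked; under the CRF, a patient graded IV is not asked. Data Collection tells collectors to use both documents together, so they must be reconciled. The composite survives this, because a highest grade of IIIa or above already marks an intervention or something worse.

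**Effect on the rate.** Let N be the cohort and T the number with a true one-year textbook outcome. Let x be the number whose only failure is untraced late imaging, and y the number classed as failures only because of a planned readmission.

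Reported rate = (T + x − y) / N, so error = (x − y) / N.

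With N = 15,000 (Data Analysis & Sample Size), one percentage point corresponds to 0.01 × 15,000 = 150 patients in x or y. The document gives neither x nor y, so neither the size nor the sign of the error can be derived.

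**The case against.** The strongest reply has four parts.

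- **Readmission.** The endpoint says only readmission, not unplanned readmission, so a one-year count of one or more satisfies its wording. This stands as far as it goes: a readmission component can be formed at one year. It is not the one formed at 30 days, so the two rates are not comparable.
- **ERCP.** A reader might infer that all late ERCP is missed. The document does not support this. Therapeutic endoscopy is at least CD IIIa under Appendix D, and ERCP for a bile duct injury found within one year has its own dated field. Only diagnostic ERCP and other imaging without intervention are lost.
- **Re-operation.** A reader might infer that the one-year form asks at the wrong grade and so loses re-operations. The CRF uses IIIb at both time points; the CD IV prompt is in the dictionary alone. IIIb is itself defined by intervention under general anaesthetic, so the grade carries the information.
- **Early deaths.** A reader might infer that 30-day deaths drop out of the one-year rate. The exclusion concerns further data collection only. Death and its day are in the 30-day record and can be carried forward, and nowhere is the one-year denominator said to be the returned one-year forms. Even if they were dropped by mistake, the effect would be small. Assuming 80% success (12,000 of 15,000) and 30-day mortality of 0.1% to 1% (15 to 150 deaths), the rate would move from 80.0% to 12,000/14,985 = 80.1%, or at most to 12,000/14,850 = 80.8%.

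None of this supplies the missing imaging data or separates planned from unplanned readmissions.

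**Conclusion.** The point holds for two components. On the listed definition, the one-year textbook outcome cannot be computed for the general cohort, because imaging after day 30 is not collected. Its readmission part can be computed only under a wider definition than at 30 days. The first gap overstates one-year success and the second understates it, so the net direction is unknown.

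It would be tempting to put a number on the imaging gap. If 2% to 5% of patients first had imaging or ERCP between day 31 and one year, that would be 300 to 750 of 15,000. The percentages are assumptions with no basis in the document. They also pool ERCP that the CD grade already captures, and they assume that none of these patients fails on any other component. The figure is a ceiling under those assumptions and should not be used as an estimate.

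The re-operation prompt is a mismatch between CRF and dictionary that does not block the endpoint. Early deaths are at most a matter of stating the denominator. The consequence is confined to one secondary endpoint and its comparison over time and between settings; a correction is worth making.

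**What to change.** Either of two changes resolves the main point.

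1. Add two fields to the one-year section of both the CRF and the dictionary: unplanned re-imaging with modality, day 31 to one year; and unplanned readmission, day 31 to one year. Use the same definitions as at 30 days.
2. Or restate the one-year endpoint as a reduced composite, without imaging and with all-cause readmission, and say that it will not be compared directly with the 30-day rate. If one-year collection has closed (Table 1 has the last period ending on 19 November 2024) and records cannot be revisited, this is the only option left.

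In either case, align the one-year re-operation prompt between CRF and dictionary in grade and in wording. For clarity, add one sentence stating that 30-day deaths and other 30-day failures count as one-year failures, over all recruited patients.

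The cost of the first option is two extra items per patient taken from routine records. The second costs no data collection but gives up the like-for-like comparison. The remaining edits are a line each.
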